### \* Located at

### 9.0 ANCILLARY TREATMENT/SUPPORTIVE CARE

This is a prevention trial. If the patient clinically requires hydration and hospitalization, all appropriate supportive measures should be used.

#### 10.0 ADVERSE EVENT (AE) REPORTING AND MONITORING

#### **10.1** Adverse Event Characteristics

**CTCAE term (AE description) and grade:** The descriptions and grading scales found in the revised NCI Common Terminology Criteria for Adverse Events (CTCAE) version 4.0 will be utilized for expedited AE reporting. However, CTCAE v5.0 must be used for serious AE reporting through CTEP-AERS as of April 1, 2018. All appropriate treatment areas should have access to a copy of the CTCAE version 5.0. A copy of the CTCAE version 5.0 can be downloaded from the CTEP web site:

**10.1.1** Adverse event monitoring and reporting is a routine part of every clinical trial. First, identify and grade the severity of the event using the CTCAE. Next, determine whether the event is expected or unexpected (see Section 10.2) and if the adverse event is related to the medical treatment or procedure (see Section 10.3). With this information, determine whether the event must be reported as an expedited report (see Section 10.4). Important: Expedited adverse event reporting requires submission of an Adverse Event Reporting System (CTEP-AERS) report(s). Expedited reports are to be completed within the timeframes and via the mechanisms specified in Sections 10.4 and 10.5. The descriptions and grading scales found in the revised NCI Common Terminology Criteria for Adverse Events (CTCAE) version 5.0 will be utilized for expedited AE reporting beginning April 1, 2018. All appropriate treatment areas should have access to a copy of the CTCAE version 5.0. A copy of the CTCAE version 5.0 be downloaded from the CTEP can website: AEs All reported via expedited mechanisms must also be reported via the routine data reporting

mechanisms defined by the protocol (see Sections 10.5 and the schedule of forms).

- 10.1.2 Each CTCAE term in the current version is a unique representation of a specific event used for medical documentation and scientific analysis and is a single MedDRA Lowest Level Term (LLT). Grade is an essential element of the guidelines and, in general, relates to severity for the purposes of regulatory reporting to NCI.
  - **NOTE**: A severe AE, as defined by the above grading scale, is NOT the same as serious AE which is defined in the table in Section 10.4.

#### **10.2** Expected vs. Unexpected Adverse Events (AEs)

The determination of whether an AE is expected is based on agent-specific information provided in Section 15.0 of the protocol.

Unexpected AEs are those not listed in the agent-specific information provided in Section 15.0 of the protocol.

**NOTE**: "Unexpected adverse events" means any adverse event that is identified in nature, severity, or frequency of risk in the information neither provided for IRB review nor mentioned in the consent form.

#### **10.3** Assessment of Attribution

**10.3.1** When assessing whether an adverse event is related to a medical treatment or procedure, the following attribution categories are utilized:

Definite - The adverse event is clearly related to the agent(s).

Probable - The adverse event is likely related to the agent(s).

Possible - The adverse event may be related to the agent(s).

Unlikely - The adverse event is doubtfully related to the agent(s).

Unrelated - The adverse event is clearly NOT related to the agent(s).

Events determined to be possibly, probably or definitely attributed to a medical treatment suggest there is evidence to indicate a causal relationship between the drug and the adverse event.

#### 10.3.2 Persistent or Significant Disabilities/Incapacities

Any AE that results in persistent or significant incapacity or substantial disruption of the ability to conduct normal life functions (formerly referred to as disabilities), congenital anomalies or birth defects, must be reported immediately if they occur at any time following treatment with an agent under an IND/IDE since they are considered to be a serious AE and must be reported to the sponsor as specified in 21 CFR 312.64(b).

#### 10.3.3 Death

Note: A death on study requires both routine and expedited reporting, regardless of causality. Attribution to treatment or other cause must be provided.

- Death due to progressive disease should be reported as **Grade 5 "Disease progression"** in the system organ class (SOC) "General disorders and administration site conditions." Evidence that the death was a manifestation of underlying disease (e.g., radiological changes suggesting tumor growth or progression: clinical deterioration associated with a disease process) should be submitted.
- Any death occurring within 30 days of the last dose, regardless of attribution to an agent/intervention under an IND/IDE requires expedited reporting within 24-hours.
- Any death occurring greater than 30 days with an attribution of possible, probable, or definite to an agent/intervention under an IND/IDE requires expedited reporting within 24-hours.
- Pregnancy loss: Pregnancy loss is defined in CTCAE as "Death in utero." Any Pregnancy loss should be reported expeditiously, as Grade 4 "Pregnancy loss" under the Pregnancy, puerperium and perinatal conditions SOC. A Pregnancy loss should NOT be reported as a Grade 5 event under the Pregnancy, puerperium and perinatal conditions SOC, as currently CTEP-AERS recognizes this event as a patient death.
- Death Neonatal: A neonatal death should be reported expeditiously as Grade 4, "Death neonatal" under the General disorders and administration SOC.

**10.4** Expedited Reporting Requirements for Studies using Commercial Agent(s) ONLY:

# 10.4.1 Expedited Reporting Requirements for Adverse Events that Occur in a Non-IND/IDE trial within 30 Days of the Last Administration of a Commercial Agent .

#### FDA REPORTING REQUIREMENTS FOR SERIOUS ADVERSE EVENTS (21 CFR Part 312)

**NOTE:** Investigators MUST immediately report to the sponsor (NCI) ANY Serious Adverse Events, whether or not they are considered related to the investigational agent(s)/intervention (21 CFR 312.64)

An adverse event is considered serious if it results in ANY of the following outcomes:

- 1) Death
- 2) A life-threatening adverse event
- An adverse event that results in inpatient hospitalization or prolongation of existing hospitalization for ≥ 24 hours
- 4) A persistent or significant incapacity or substantial disruption of the ability to conduct normal life functions
- 5) A congenital anomaly/birth defect.
- 6) Important Medical Events (IME) that may not result in death, be life threatening, or require hospitalization may be considered serious when, based upon medical judgment, they may jeopardize the patient or subject and may require medical or surgical intervention to prevent one of the outcomes listed in this definition. (FDA, 21 CFR 312.32; ICH E2A and ICH E6).

ALL SERIOUS adverse events that meet the above criteria MUST be immediately reported to the NCI via CTEP-AERS within the timeframes detailed in the table below.

| Hospitalization                               | • Grade 1
Timeframes | • Grade 2
Timeframes | • Grade 3
Timeframes | Grade 4 & 5
Timeframes |
|---|-------------------------|-------------------------|-------------------------|---------------------------|
| Resulting in Hospitalization $\ge 24$ hrs     | 10 Calendar Days        |                         |                         | 24-Hour;                  |
| Not resulting in Hospitalization $\ge 24$ hrs | Not required            |                         | 10 Calendar
Days     | 5 Calendar Days           |

**NOTE**: Protocol specific exceptions to expedited reporting of serious adverse events are found in the Specific Protocol Exceptions to Expedited Reporting (SPEER) portion of the CAEPR **Expedited AE reporting timelines are defined as:** 

- ° "24-Hour; 5 Calendar Days" The AE must initially be reported via CTEP-AERS ≤ 24 hours of learning of the AE, followed by a complete expedited report ≤ 5 calendar days of the initial 24-hour report.
- "10 Calendar Days" A complete expedited report on the AE must be submitted ≤ 10 calendar days of learning of the AE.

 Serious adverse events that occur more than 30 days after the last administration of investigational agent/intervention and have an attribution of possible, probable, or definite require reporting as follows:

#### Expedited 24-hour notification followed by complete report $\leq$ 5 calendar days for:

• All Grade 4, and Grade 5 AEs

Expedited 10 calendar day reports for:

• Grade 2 adverse events resulting in hospitalization or prolongation of hospitalization

- Grade 3 adverse events
-  For studies using PET or SPECT IND agents, the AE reporting period is limited to 10 radioactive half lives, rounded UP to the nearest whole day, after the agent/intervention was last administered. Footnote "1" above applies after this reporting period.

Refer to Section 10.4.3 for NCI Contact Information or Technical Help regarding CTEP-AERS reporting.

#### 10.4.2 Additional Instructions or Exceptions to Adverse Event Reporting System (CTEP-AERS) Reporting Requirements:

The Alliance SAE Coordinator will forward a copy of all CTEP-AERS reports to the Alliance IND Coordinator who will notify the FDA as warranted by the event and stipulated in the U.S. Code of Federal Regulations.

In the rare event when internet connectivity is disrupted, a 24 hour notification must be made to NCI by telephone. An electronic report must be submitted immediately upon establishment of internet re-connection.

#### 10.5 Other Required Event Reporting

| Event Type   | REPORTING PROCEDURE   |
|--|---|
| Other Grade 4 or 5 Events and/or Any
Hospitalizations During Treatment Not
Otherwise Warranting an Expedited
Report | Complete the Grade 4 or 5 Non-AER Reportable
Events/Hospitalization Form electronically via the Remote Data
Entry System within 5 working days of the date the Clinical
Research Associate (CRA) is aware of the event(s)
necessitating the form.
If an CTEP-AERS report has been submitted, this form does not
need to be submitted. |

| System Organ Class         |                              |          | Each       |
|----------------------------|------------------------------|----------|------------|
| (SOC)                      | Adverse event                | Baseline | evaluation |
| Gastrointestinal disorders | Abdominal distension         | Х        | Х          |
|                            | Bloating                     | Х        | Х          |
|                            | Diarrhea                     | Х        | Х          |
|                            | Nausea                       | Х        | Х          |
|                            | Vomiting                     | Х        | Х          |
|                            | Gastrointestinal disorders - | Х        | Х          |
|                            | Other, specify               |          |            |
|                            | Gastrointestinal disorders   | Х        |            |
|                            | – Other, # of stools / day   |          |            |

**10.5.1** Adverse events to be graded at each evaluation and pretreatment symptoms/conditions to be evaluated at baseline per CTCAE v4.0 grading unless otherwise stated in the table below:

- **10.5.2** Submit via appropriate Alliance Case Report Forms (i.e., paper or electronic, as applicable) the following AEs experienced by a patient and not specified in Section 10.5.1.
  - **10.5.2.1** Grade 2 AEs deemed *possibly*, *probably*, *or definitely* related to the study treatment or procedure.
  - **10.5.2.2** Grade 3 and 4 AEs regardless of attribution to the study treatment or procedure.
  - **10.5.2.3** Grade 5 AEs (Deaths)
    - Any death within 30 days of the patient's last study treatment or procedure regardless of attribution to the study treatment or procedure.
    - Any death more than 30 days after the patient's last study treatment or procedure that is felt to be at least possibly treatment related must also be submitted as a Grade 5 AE, with a CTCAE type and attribution assigned.
- **10.5.3** Refer to the instructions in the Forms Packet (or electronic data entry screens, as applicable) regarding the submission of late occurring AEs following completion of the Active Monitoring Phase (i.e., compliance with Test Schedule in Section 4.0).

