#### 1.3.6 Rationale for Metformin Dose

Our rationale for dose selection was to maximize bioavailability and the opportunity to observe efficacy for this new indication, while minimizing toxicity and adverse events in this cohort, based on earlier studies where metformin was used in other indications and age groups.

There is evidence that the use of metformin in individuals with "normal" insulin levels appears to be safe and it reduces insulin levels. Studies by Goodwin *et al.* show that in breast cancer patients given metformin (1500 mg/day), the mean baseline fasting insulin level was in the "normal" range (75.7 pmol/L) and only one woman had an insulin level above 140 pmol/L (the level was 150 pmol/L). Insulin levels were reduced by 22% without the occurrence of hypoglycemia. Similar safety and insulin-lowering effects of metformin have been reported in non-diabetic, non-breast cancer subjects with normal insulin levels.

In a recent study of polycystic ovary syndrome (PCOS), metformin (2250 mg/day) lowered fasting insulin levels by 18% from a mean baseline insulin of 64.5 pmol/L in women in the lowest quartile of baseline insulin (greater reductions were seen in women with insulin levels markedly above normal). Similar results in PCOS subjects were reported by Roumaldi (mean baseline fasting insulin 47.0 pmol/L, 15% reduction after metformin at a low dose of 1000 mg/day for 6 months). Based on these observations, we anticipate that metformin will safely lower insulin levels but not promote significant hypoglycemia.

There is clinical evidence that fasting insulin levels are associated with poor breast cancer outcomes. We have chosen a dose of metformin for breast cancer prevention that mirrors MA-32, an ongoing adjuvant multicenter trial of metformin vs. placebo in women with breast cancer. At the dose we propose Metformin safely lowers insulin levels by about 20% in 1) non-diabetic women with breast cancer and 2) women without cancer who have baseline fasting insulin levels in the normal range. Evidence in observational, non-interventional trials suggests that metformin use in diabetics may reduce cancer risk and mortality in women receiving chemotherapy for breast cancer. We hypothesize that the dose of metformin we propose will reduce breast cancer risk through its secondary targeting of insulin/Complex 1 and primary targeting of AMPK/Akt/mTOR.

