- **15.1.7 Known potential toxicities:** Metformin is considered to have a favorable safety profile in diabetes mellitus patients. In a US double-blind clinical trial for patient with type 2 diabetes, gastrointestinal symptoms such as diarrhea, nausea and vomiting, abdominal discomfort, flatulence, indigestion, and asthenia were the most common reactions to the drug. These symptoms were dose-dependent, transient, and resolved spontaneously with continued use. The drug may cause GI upset so should be taken with food. Additional adverse reactions reported in 1 to 5% of subjects were abnormal stools, hypoglycemia, myalgia, lightheadedness, dyspnea, nail disorder, rash, increased sweating, taste disorder, chest discomfort, chills, flu syndrome, flushing and palpitation. A recently published trial of patients with type 2 diabetes mellitus reported a vitamin B12 deficiency with long term treatment. Lactic acidosis is a rare, but serious, metabolic complication that can occur due to metformin accumulation during treatment. Reported incidence of lactic acidosis in patients with significant renal insufficiency.
- **15.1.8 Drug procurement:** Metformin Hydrochloride 850 mg tablets will be purchased for use in the trial. Placebo tablets that are similar in size and color will also be purchased. The metformin and placebo tablets will be bottled and labeled by Pharm Ops, Inc. The bottles will be labeled so that study participants, caregivers, and investigators are blinded to the contents.

Blinded metformin/placebo: Patient-specific supplies of metformin/placebo will be ordered by the registering institution after each patient is enrolled to the study.

Fax or email the Alliance A211102 Drug Order Form to:

Patients will need to return to the clinic to receive additional supplies of blinded drug at 3, 6, and 9 months after registration. Sites may dispense a 6 month supply. However, sites that dispense a 6 month supply will be responsible for reconciliation of all medication returns. Institutional staff will contact the Registration Office for a study medication code number. Drug orders for these additional supplies should be submitted at least one week prior to each of these visits using the Alliance A211102 Drug Order Form.

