# 16.2.2.5 Record and analyze patient-reported knowledge of the arm to which they were randomized:

In March, 2019 the study team was notified of an unexpected unblinding incident. An enrolled patient informed her physician that she was able to google the code (serial number) on the pills to uncover whether she was taking metformin or placebo. Notably, all metformin tablets have a serial number printed on them while the placebo pills do not have any such information; in other words, the placebo tablets were not designed to look exactly like the metformin tablets and the risk of potential unblinding due to the lack of similarity was known prior to study activation, and this risk was deemed acceptable. The Division of Cancer Prevention at NCI and the Alliance Data and Safety Monitoring Board were notified of this single unblinding incident.

Because the primary outcome is an objective measurement, the trial results are not at significant risk of bias due to the single known incident of unblinding. Furthermore, the remaining secondary, tertiary, and correlative endpoints are not subjective in nature. Coupled with the fact that this study is intended to serve as proof of principle for the use of RPFNA to test for the presence or absence of atypia before, during, and after the administration of a prevention agent, this unblinding incident is unlikely to affect the validity of the study.

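### Non-GI Grade 2 adverse events are recorded only if judged treatment-related, so their counts can differ between arms through attribution when the arm is known

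*Combined protocol and SAP*

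**What the plan says.** Section 10.5.1 lists the events graded at baseline and at each evaluation. All are gastrointestinal. Section 10.5.2 then covers "the following AEs experienced by a patient and not specified in Section 10.5.1". Within it, Grade 2 is limited to "Grade 2 AEs deemed *possibly*, *probably*, *or definitely* related to the study treatment or procedure", while the next item takes "Grade 3 and 4 AEs regardless of attribution to the study treatment or procedure". Deaths within 30 days of the last treatment are taken whatever the cause, and later deaths if at least possibly related. Grade 1 is not mentioned. Separately, Section 10.4.1 requires expedited reports of serious events whether or not related, including Grade 1 and 2 events with a hospital stay of 24 hours or more, and Section 10.5 has a form for other hospitalizations during treatment.

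On the blind, Section 16.2.2.5 says that "all metformin tablets have a serial number printed on them while the placebo pills do not have any such information". It adds that the risk was known before activation and that one woman identified her tablets and told her physician. It concludes that bias is unlikely because the endpoints are objective, adds a question to patients about what they knew, and plans sensitivity analyses of the primary and secondary endpoints. Sections 4.0 and 7.3 have the CRA obtain the arm before the 12-month visit.

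On hypoglycemia, Section 1.3.6 states that "we anticipate that metformin will safely lower insulin levels but not promote significant hypoglycemia". Section 15.1.7 says: "Additional adverse reactions reported in 1 to 5% of subjects were abnormal stools, hypoglycemia". Section 15.1.9 asks nurses to teach patients its symptoms. It is not in the 10.5.1 table.

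**The concern.** A non-GI Grade 2 event that does not lead to hospitalization reaches the database only if someone judges it at least possibly related. Attribution is thus a filter on collection. If the person judging knows or suspects the arm, the filter can pass more events on metformin than on placebo. An event in a woman known to be on placebo is naturally called unrelated, and then it is not submitted.

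The defence in Section 16.2.2.5 speaks of endpoints and does not mention attribution. Its new question goes to patients and asks about certain knowledge, so it measures neither suspicion nor what site staff knew. The planned sensitivity analyses do not cover safety, and they could not restore events that were never submitted.

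At stake are the adverse-event reports to the DSMB (Section 16.3.1) and the final tolerability table. For a preventive agent, tolerability is part of what readers will want from the trial.

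**Working it through.** **No figure to reproduce.** The documents give no adverse-event rate, attribution rate or safety power. The check is of the rule itself, followed by an illustration with assumed rates.

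**Step 1: which events can the filter distort?**

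| Event class | Collection rule | Does attribution decide entry? |
|---|---|---|
| Listed GI terms | Graded at each evaluation (10.5.1) | No |
| Non-GI Grade 1 | Not listed in 10.5.2 | No; absent in both arms |
| Non-GI Grade 2, not hospitalized | Only if at least possibly related (10.5.2.1) | **Yes** |
| Non-GI Grade 3-4 | All (10.5.2.2) | No |
| Deaths within 30 days of last treatment | All (10.5.2.3) | No |
| Serious events within 30 days of last dose, and hospitalizations during treatment | All (10.4.1, 10.5) | No |

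**Step 2: can the arm be known when attribution is made?** There are two routes.
- Tablets: a woman can identify hers and tell staff. One case is documented.
- Schedule: Section 4.0 places adverse-event assessment at the end of ramp-up and at 6, 12 and 24 months. The CRA has the arm before the 12-month visit. An event from the blinded second half-year that first comes up at that visit can be attributed with the arm known. Supply visits (Section 15.1.8) may pick up some events earlier, but no adverse-event assessment is scheduled at months 3 or 9.

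**Step 3: effect of the filter.** Let n be women per arm, t the true incidence (equal in both arms), and a_M and a_P the probabilities that an event is called related on metformin and on placebo.
- Expected recorded count = n × t × a.
- Recorded risk ratio = (t × a_M) / (t × a_P) = a_M / a_P, whatever t is.

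**Step 4: illustration.** n = 96 / 2 = 48 (Section 16.1.1, equal arms). Assume t = 20%. The last column is the chance that a two-sided 5% chi-square test would be nominally significant, by exact enumeration of two binomials.

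| Attribution, metformin / placebo | Recorded women | Risk ratio | Chance of significance |
|---|---|---|---|
| No filter | 9.6 v 9.6 | 1.0 | 5.2% |
| 50% / 50% | 4.8 v 4.8 | 1.0 | 5.9% |
| 60% / 40% | 5.8 v 3.8 | 1.5 | 11.2% |
| 70% / 30% | 6.7 v 2.9 | 2.3 | 28.0% |
| 80% / 20% | 7.7 v 1.9 | 4.0 | 55.5% |

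For example, 48 × 0.20 × 0.70 = 6.7 and 48 × 0.20 × 0.30 = 2.9. At 70% / 30%, moving t from 5% to 40% moves the last column from 4.5% to 51.4%.

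**Step 5: partial knowledge of the arm.** Assume t = 30% and attribution of 50% if metformin is known, 20% if placebo is known, and 35% if blinded. With a share k knowing, the recorded gap is 0.30 × k × (0.50 − 0.20).
- k = 100%: 15.0% v 6.0%, a gap of 9.0 points (48 × 0.090 = 4.3 women).
- k = 30%: 11.85% v 9.15%, a gap of 2.7 points (1.3 women).
- k = 1%, about one woman in 96: a gap of 0.09 points (0.04 women).

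**Step 6: hypoglycemia alone.** Applying the 1 to 5% of Section 15.1.7 as an assumption gives 48 × 0.01 = 0.5 to 48 × 0.05 = 2.4 women per arm, all grades. At 5% and 70% / 30% attribution, 1.7 v 0.7 would be recorded. Counts this small settle little either way, but the filter can remove much of what there is to see.

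**The case against.** The case against is substantial.

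- **The affected class is narrow.** A reader might infer that all non-GI toxicity counts are open to this bias, or that leaving out Grade 1 adds to it. Neither follows. Step 1 leaves only non-hospitalized, non-GI Grade 2 events, and the Grade 1 omission applies alike in both arms: it loses information but creates no difference. This stands.
- **The path from tablet to attribution is indirect.** The tablets reveal the arm to the woman, who has no stated role in attribution. Bottles are labelled to keep investigators and caregivers blind, one incident is known, and balanced discontinuation is offered as a sign of limited scope. This stands as a limit on size for the tablet route. It does not answer the scheduled route, which reaches the site for every woman still in follow-up at 12 months. How many events first surface at that visit, and whether the person attributing them has been told the arm, the documents do not say.
- **The threshold is low.** Possible means only that the event may be related (Section 10.3.1), and hypoglycemia is a listed reaction, so a blinded assessor would rarely go below it. True under blinding, but not once placebo is known.
- **The hypoglycemia expectation can still be checked.** A reader might infer that the expectation in Section 1.3.6 is untestable. It concerns significant hypoglycemia, which Grade 3-4 reporting would largely catch, and fasting glucose is measured in both arms. Episodes below Grade 3 between visits are what may be missed. The statement is also dose rationale rather than a hypothesis of the trial.
- **No inference depends on it.** There is no safety objective in Section 2.0 and no planned between-arm adverse-event test. This stands. Nor does Section 16.2.2.5 contradict itself: its claim is about endpoints, and attribution is not one.

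**Conclusion.** The mechanism holds. The counts of non-hospitalized, non-GI Grade 2 events, hypoglycemia among them, can differ between arms through attribution rather than true incidence, because attribution decides entry and the arm can be known when it is made.

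The size is unknown. That the recorded risk ratio equals the ratio of attribution probabilities rests only on equal true incidence; every other figure above rests on assumed rates. A gap as wide as 15% v 6% needs the arm to be known for every attribution all year, which no section supports. At the level of the single known tablet incident, the effect is negligible.

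This is an avoidable weakness in the safety tables and DSMB reports, worth correcting because it is cheap. It does not touch the primary endpoint.

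**What to change.** 1. Add hypoglycemia to the 10.5.1 table, at baseline and each evaluation.
2. In 10.5.2.1, for the 12 blinded months, record Grade 2 events whatever their attribution, and keep attribution as a data field.
3. Do not mix the two collection rules. For women whose whole blinded year falls under the new rule, tabulate month 0-12 events by arm without regard to attribution. For women followed before the change, limit that comparison to Grade 3 and above plus the solicited GI terms, and note in the table that their non-GI Grade 2 counts were filtered by attribution.

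The cost is modest extra entry on existing forms in a trial of 96 women, and one added row. Past Grade 2 events cannot be fully recovered, and women already randomized have no solicited hypoglycemia baseline. If few women remain in the blinded year, the note in the safety table is the main gain. The change removes the filter but does not restore the blind: reporting and grading can still be influenced by knowledge of the arm.
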